Appendix D8: Safety

Adverse Events

Adverse event type	Digoxin		Bisoprolol		Total	
	N (%) of pts (N=)	N of Events	N (%) of pts (N=)	N of Events	N (%) of pts (N=)	N of Events
Gastrointestinal upset						
Blurred vision						
Rash						
Peripheral oedema						
Symptomatic bradycardia						
Dizziness						
Headache						
Lethargy						
Upper respiratory tract symptoms						
Symptomatic hypotension						
Other						
Total	-	xx	-	xx	-	xx
N of pts with at least one AE	xx (xx%)		xx (xx%)		xx (xx%)	
Chi² test for difference in number of patients with at least one AE between treatment groups P-value = x.xxx						

SAE's

SAE's	Digoxin (N=)	Bisoprolol (N=)	Total (N=)	Chi ² Test P-value
Patients with at least one SAE:				
No				
Yes				
No of patients exactly with:				
1 SAE				-
2 SAE's				-
... SAE's				-
Total number of SAE's				-

- List of all SAE's

GP visits by trial arm at 6 and 12 months

GP visits	Digoxin (N=)	Bisoprolol (N=)	Total (N=)
6 months follow-up			
Has the patient seen their GP since last trial visit? No Yes Missing			
If yes, how many times: N Mean [SD] Median {IQR} Min-Max			
Total number of visits for all patients			
12 months follow-up			
Has the patient seen their GP since last trial visit? No Yes Missing			
If yes, how many times: N Mean [SD] Median {IQR} Min-Max			
Total number of visits for all patients			

Number of patients that had pauses and duration of pause (from the 24 hour tape form)

Pauses and duration from 24-hour tape	Digoxin (N=)	Bisoprolol (N=)	Total (N=)
Did the patient have any pauses? No Yes Missing			
If yes, maximal pause duration (seconds): N Mean [SD] Median {IQR} Min-Max			

Digoxin levels at 6 and 12 months for Digoxin arm

Digoxin levels (ug/l)	6 months	12 months
N Mean [SD] Median {IQR} Min-Max		

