12.3 Statistical analysis

A separate Statistical Analysis Plan for the RATE-AF trial provides a detailed description of the planned statistical analyses. A brief outline of these analyses is given below.

The primary comparison groups will be composed of those who are randomised to digoxin group and those randomised to the beta-blockers group. All analyses will be based on the intention to

treat principle, with all patients analysed in the arms to which they were allocated irrespective of compliance with the randomised allocated treatment, and all patients will be included in the analyses. We will, as a sensitivity analysis, conduct per-protocol analyses, where appropriate.

For all analyses, a p-value <0.05 will be considered statistically significant.

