12.3.2 Feasibility and Secondary outcomes analysis

The feasibility and secondary outcomes for the trial comprise of a combination of both continuous and categorical (dichotomous) data items.

Categorical endpoints:

For outcomes which are categorical (dichotomous) in nature, the proportion of participants and percentages will be analysed between arms.

Logistic/Log-binomial regression models will be fitted (where appropriate) to adjust for treatment arm, baseline scores and all minimisation variables.

Results will be presented as odds ratios/relative risks and 95% confidence intervals.

Continuous endpoints:

Any outcomes that are continuous in nature will be analysed in the same way as the primary outcome.

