4.7. Sample size

Randomising 144 patients we can assume an 85% power to detect an effect size of half a standard deviation in a continuous outcome measure of QoL (two-sided alpha of 0.05).

A sample size of 160 patients would account for an estimated 10% loss to follow-up (including withdrawal and death prior to 12-month assessment).

There is some evidence from existing research to support the notion that the treatment effect could be this large. The mean SF-36 role-physical score from the rate-control arm of the RACE study was 47, with a 17% improvement with rate-control over time.² In another study, CCB resulted in 22% improvement in a proprietary symptom-checklist, compared to a non-significant 8% change in those assigned to beta-blockers (SD 10-points in both groups). These values are also consistent with a 17% improvement in SF-36 scores in a third trial, PIAF.³

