5.1. Confidence intervals and p-values

All estimates of differences between groups will be presented with two-sided 95% confidence intervals, unless otherwise stated. P-values will be reported from two-sided tests.

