9.1. Covariate adjustment

In the first instance, intervention effects between groups for all outcomes will be adjusted for the baseline score (where appropriate), minimisation parameters (Gender, baseline EHRA) as well as age at randomisation and

baseline LVEF (as continuous variables). The minimisation variable EHRA is a categorical score with the following categories (1, 2a, 2b, 3, 4) and for minimisation, this score was categorised into (class 1, 2a) and (class 2b, 3, 4). However for the analysis we will be adjusting this variable in its original 5 categorical form.

The Bisoprolol arm will be used as a reference category for all model based analyses.

For some binary outcomes, sometimes the effect size to be estimated of interest is the relative risk rather than the odds ratio and so for these outcomes, a log-binomial model is often used. However there are convergence issues with this type of model and so if the log-binomial model fails to converge, a Poisson regression model with robust standard errors will be used to estimate the same parameters.⁷ If this also fails to converge, unadjusted estimates will be produced from the log-binomial model. It will be made clear in the final report why this occurred (e.g. not possible due to low event rate/lack of model convergence).

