9.8. Safety data

The number and percentage of participants experiencing any adverse events, serious adverse events (SAEs) and suspected unexpected serious adverse reactions (SUSARs) will be presented by treatment arm. A table listing all the SAEs will be provided.

The safety data will also include summaries by treatment arm for:

- Digoxin levels at 6 and 12 months
- Number of patients requiring pacemaker implantation
- Unplanned hospitalisation rates (from the SAE form)
- Number of patients that had pauses and duration of pause (from the 24 hour tape form)
- All cardiovascular events (as recorded in the cardiovascular events form)
- Number of GP visits (from the GP form)

A template for reporting this data is given in Appendix D8.

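### The safety tables compare the arms on any AE and any SAE by chi-squared p-value alone, without an effect estimate or confidence interval

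*SAP*

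**What the plan says.** SAP 9.8 is descriptive. It says that the numbers and percentages of participants with adverse events, SAEs and "suspected unexpected serious adverse reactions (SUSARs) will be presented by treatment arm. A table listing all the SAEs will be provided". It names no test, effect measure or interval.

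The templates in SAP Appendix D8 go further. The adverse-event table ends with a "Chi² test for difference in number of patients with at least one AE between treatment groups", and the SAE table has a chi-squared p-value column for patients with at least one SAE. No column holds a risk difference, relative risk, odds ratio or confidence interval. The other D8 tables (GP visits, pauses, digoxin levels) are descriptive. SAP 9.6 rules out formal modelling for the feasibility outcomes, which include cardiovascular events, unplanned hospitalisation and discontinuation for adverse reactions. The two chi-squared tests are therefore the only between-arm safety inference in the plan.

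On general principles, SAP 5.1 attaches two-sided 95% confidence intervals to estimates of group differences and adds "P-values will be reported from two-sided tests". Protocol 12.3 states "For all analyses, a p-value <0.05 will be considered statistically significant".

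**The concern.** A test with no estimate beside it shows only whether a difference reached a threshold. It does not show how large an excess of events the data still allow, which is the main question for a safety table comparing two drugs. The trial was sized on a quality-of-life score, so a non-significant safety test is likely even if one arm carries a real excess. Nothing in D8 tells the reader how little such a result excludes.

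The format is also out of line with the rest of the SAP. The comparisons in D5, D6 and D9 are laid out as an adjusted difference, odds ratio or ratio of geometric means with its 95% interval. SAP 5.1 shows the same intention. D8 does not literally break that rule, because it specifies no estimate to which an interval could attach. SAP 9.8 and D8 also disagree on whether any test is planned.

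**Working it through.** **Inputs from the documents.** Allocation is 1:1 (SAP 4.6). On numbers, "A sample size of 160 patients would account for an estimated 10% loss to follow-up" (SAP 4.7), so 80 per arm are randomised and 72 per arm remain after 10% loss. Safety is analysed by intention to treat (SAP 5.3), so 80 per arm is the main case. Tests are two-sided (SAP 5.1) at 0.05 (protocol 12.3).

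**Assumption.** The documents give no AE or SAE rates. The lower-arm rate is varied from 5% to 85%, with the other arm 10 points higher.

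**The plan's own figure.** n per arm = 2(1.960 + 1.036)² / 0.5² = 71.8, rounded up to 72, so 144 in total; 144 / 0.9 = 160. The stated 85% power for 0.5 SD reproduces. It concerns quality of life only; the documents give no power for a safety comparison.

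**Power of the chi-squared test.** Power = Φ{ [ |p2 − p1|√n − 1.96√(2p̄(1 − p̄)) ] / √[ p1(1 − p1) + p2(1 − p2) ] }, with p̄ the mean of p1 and p2.

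For 20% vs 30% with n = 80: [0.1 × 8.944 − 1.96 × √0.375] / √0.37 = (0.894 − 1.200) / 0.608 = −0.503, so power is 31% and the miss rate 69%.

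| True rates | Miss rate, formula | Miss rate, exact enumeration |
|---|---|---|
| 5% vs 15% | 44% | 43% |
| 10% vs 20% | 58% | 58% |
| 20% vs 30% | 69% | 69% |
| 40% vs 50% | 76% | 76% |
| 50% vs 60% | 76% | 76% |
| 80% vs 90% | 58% | 58% |
| 85% vs 95% | 44% | 43% |

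At 72 per arm the formula gives 61% (10% vs 20%) to 78% (45% vs 55%). With a continuity correction at 80 per arm, the miss rate is 66% to 81% for lower-arm rates of 10% to 80%. For 80% power to detect 10 points, 199 per arm would be needed at 10% vs 20%, 294 at 20% vs 30% and 388 at 40% vs 50%.

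**What an interval would add: two illustrative tables with invented counts.**

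- 16/80 vs 23/80. Chi-squared p = 0.20. Risk difference 8.75 points, SE √(0.2 × 0.8/80 + 0.2875 × 0.7125/80) = 6.75 points, 95% CI −4.5 to +22.0. RR 1.44, SE of log RR √(1/16 + 1/23 − 2/80) = 0.285, 95% CI 0.82 to 2.51.
- 40/80 vs 46/80. Chi-squared p = 0.34. Risk difference 7.5 points, SE 7.86 points, 95% CI −7.9 to +22.9. RR 1.15, SE of log RR √(1/40 + 1/46 − 2/80) = 0.147, 95% CI 0.86 to 1.54.

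Both are non-significant, yet the first leaves a doubling of risk open and the second excludes it. The p-value does not separate them; the intervals do.

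**The case against.** The strongest reply is that the harm is inferred. A reader might conclude that the plan will treat p>0.05 as equal safety. The documents do not say so: protocol 12.3 defines when a result is significant, not what a non-significant one means. That stands. The point is only that nothing in the plan guards against the reading.

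A reader might also hold that D8 breaks the plan's rules. It mostly does not. Protocol 12.3.2 does say "Results will be presented as odds ratios/relative risks and 95% confidence intervals", but for feasibility and secondary outcomes, and any AE and any SAE are in neither list. SAP 5.3 fixes the analysis population, with which D8 does not conflict. SAP 9.1 speaks of adjusting all outcomes, but only in the first instance, and it names no safety outcome for its relative-risk model. Unadjusted safety tables are common, and the lack of adjustment is not the defect.

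Two stronger statements about size fail. It is not true that about 80% power is reached only for a doubling of risk: 60% vs 80% has the same 79% power as 20% vs 40%. Nor does a non-significant result always leave a doubling open, as the second table above shows.

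Limited power is also partly acknowledged. Protocol 12.2 accepts that smaller differences may be missed and looks to a larger trial for clinical event rates. That remark sits in the quality-of-life power section and does not reach the D8 tables. Finally, D8 prints counts by arm, so a reader could derive a crude interval. That softens the problem, but the plan should not leave the calculation to the reader.

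**Conclusion.** The point holds as a matter of reporting. The plan's only between-arm safety inference is two unadjusted chi-squared p-values. They appear only in a template, have no estimate or interval, and go unmentioned in SAP 9.8.

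The size depends on event rates that the documents do not give. For assumed lower-arm rates of about 10% to 80%, the chance of missing a true 10-point difference at 80 per arm is about 58% to 76%; at 5% vs 15% or 85% vs 95% it is about 43% to 44%. The miss rates show that p>0.05 would exclude little. They do not show that the trial should have been sized for safety, or that the investigators intend a claim of equal safety. The primary analysis and the conduct of the trial are unaffected, so the point is minor.

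**What to change.** In SAP 9.8 and Appendix D8, report the crude risk difference and the crude relative risk, digoxin versus bisoprolol, each with a 95% confidence interval, for patients with at least one AE and at least one SAE among all randomised patients. These can replace the chi-squared p-values or stand beside them. If the p-values stay, 9.8 should name the test so that text and template agree.

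Add a sentence saying that the trial is not powered for safety, that conclusions will rest on the confidence limits, and that p>0.05 will not be reported as absence of a difference.

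The crude estimates should be the main presentation. SAP 9.1 already provides that "if the log-binomial model fails to converge, a Poisson regression model with robust standard errors will be used to estimate the same parameters", and an adjusted relative risk from it could be optional support where event counts allow. It should not lead, for three reasons:

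- It has eight non-intercept parameters (arm, gender, age, LVEF and four EHRA terms). At 10% vs 20% there would be about 8 + 16 = 24 events, or three per parameter.
- Any patient without a baseline LVEF would drop out.
- It gives no risk difference.

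The cost is a change of SAP wording and two template edits, with no new data. The downside is that the safety table will show wide intervals: about ±11 points for the risk difference at 10% vs 20%, and ±15 at 40% vs 50%.

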Appendix D9: Subgroup analysis for primary outcome

Subgroup analysis for PCS of SF36v2 at 6 months

Subgroup	Adjusted Mean difference (95% CI)	Interaction P-value
Gender Male Female		
Modified EHRA class (1, 2a) (2b, 3, 4)		
Receiving beta-blocker therapy within 1 month of randomisation No Yes		
Age (in years) <75 years ≥75 years		
Left Ventricular Ejection Fraction (%) <50% ≥50%		

Forest plot of subgroup analysis for primary outcome
